15.5 Study Records Retention

Study records will be maintained for at least three years from the date that the grant federal financial report (FFR) is submitted to the NIH or longer as dictated by local IRB or state laws/regulations.

As outlined by IRB regulations, data will be destroyed in an appropriate and safe way after three years from the conclusion of the study. The file connecting subjects' names with their unique identification number will be kept in a password-protected file by the CC and on the GPI's computer for a minimum of three years, in accordance with IRB regulations, before being securely erased.

15.6 Protocol Deviations

A protocol deviation is any noncompliance with the clinical study protocol and good clinical practice principles. The noncompliance may be on the part of the subject, the investigator, or study staff. As a result of deviations, corrective actions are to be developed by the study staff and implemented promptly. All deviations from the protocol must be addressed in study subject source documents and promptly reported to NIDCR and the local IRB, according to their requirements.

Any protocol deviation that is reportable to an IRB must also be reported to NIDCR. NIDCR defers to the IRB for reporting time-frame requirements. Once a protocol deviation has been reported to an IRB, action must be taken to report the deviation to NIDCR. If the IRB overseeing the study protocol requires annual reporting of protocol deviations to their IRB, that reporting frequency is acceptable to NIDCR. At the time of each DSMB review, all previously unreported protocol deviations must be reported to the DSMB independent of when they are reported to IRBs.

16 PUBLICATION POLICY

This study will comply with the NIH Public Access Policy, which ensures that the public has access to the published results of NIH funded research. It requires scientists to submit final peer-reviewed journal manuscripts that arise from NIH funds to the digital archive PubMed Central upon acceptance for publication. All study personnel are required to read in its entirety and agree to abide by the network's "Data Analysis, Publications, and Presentations Policies" document. The current version of this policy is always kept at the network's public web site at http://nationaldentalpbrn.org/publication.php.

Appendix A1: Schedule of Events (Pilot Phase)

For this study, a dental exam will be performed and if the patient qualifies, he/she will be presented with the consent form. If participating, the practitioner will fill out the pre-treatment questionnaire, use the device (if in the device arm), and complete the post-treatment questionnaire. The questionnaire includes questions about caries risk, demographic and lesion characteristics, and final treatment.

Procedures	Pre enrollment (S -0)	Baseline (S0)	Pre-intervention Phase (S1=Complete within approx. 2 weeks following S0)	Intervention Phase (S2=Complete within approx.2 +_1 week following S1)	Post Intervention (S3=Complete within approx. 1 week following S2)
Practitioner Recruitment and Enrollment	Х				
Pre-Baseline Diagnostic Vignette	Х				
Practitioner and Office Staff Training		Х			
Verify Patient Inclusion Exclusion			Х	Х	
Data Collection			Х	Х	
Practitioner Randomization			Х		
Device Set up and Training (if randomized to device arm)				Х	
Post Study Diagnostic Vignette					Х
Post Study Questionnaire					Х
			Patient Ir	nvolvement	
Informed Consent			Х	Х	

Appendix A2: Schedule of Events (Full study)

For this study, a dental exam will be performed and if the patient qualifies, he/she will be presented with the consent form. If participating, the practitioner will fill out the pre-treatment questionnaire, use the device (if in the device arm), and complete the post-treatment questionnaire. The questionnaire includes questions about caries risk, demographic and lesion characteristics, and final treatment.

Procedures	Pre enrollment (S -0)	Baseline (S0)	Pre-intervention Phase (S1=Complete within approx. 6 weeks following S0)	Intervention Phase (S2=Complete within approx.8 +_2 weeks following S1)	Post Intervention (S3=Complete within approx. 2 weeks following S2)
Practitioner Recruitment and Enrollment	х				
Pre-Baseline Diagnostic Vignette	Х				
Practitioner and Office Staff Training		Х			
Verify Patient Inclusion Exclusion			Х	Х	
Data Collection			Х	Х	
Practitioner Randomization			Х		
Device Set up and Training (if randomized to device arm)				Х	
Post Study Diagnostic Vignette					Х
Post Study Questionnaire					Х
			Patient Ir	nvolvement	
Informed Consent			Х	Х	

Appendix B: Quality Management Plan

This Study Quality Management Plan organizes the plans for QA/QC across the SOCL Study Protocol Study Timeline and Study Activities. Some of the planned QA/QC is described in the main text of the protocol. Specifically, the QA/QC for Data Collection and Management is described in Section 13 above. The Data Management Plan described in Appendix C below will contain the specific plan for Quality Management of Data Collection and Management.

The following is a summary of the QA/QC activities that are planned for each key study activity:

1. Practitioner Recruitment, Training, and Enrollment:

- a. The RCs who will be recruiting practitioners within each region will work with the practitioners to assure that they understand the expectations of them for the study and assure the quality of practitioner recruitment and enrollment.
- b. The Study Manager will ensure the proper enrollment of practitioners and their locations' study personnel into the IRB system. Through this activity, the Study Manager will also provide QA/QC of the recruitment across regions according to the protocol and procedures, and will help troubleshoot recruitment/enrollment issues.

2. Subject screening and enrollment:

- a. Proper training of the practitioners by the RC on the protocol and procedures as outlined in the study Manual of Procedures (MOP) is a planned QA activity. This will assure that the practitioners are ready to conduct the subject screening and enrollment in accordance with the protocol.
- b. The RC will be a resource for the practitioners and study personnel to ask questions during subject screening and enrollment. The Study Manager will keep a log of problems encountered and solutions across regions and RCs. This will assure consistency of solutions to problems encountered by practices across RCs and Regions. The RC will also use the log to create a regularly updated 'Frequently Asked Questions' document that will be available to all practices, so that they have a resource for finding information and solutions for commonly encountered problems.

As the practitioners and each practice are anticipated to be busy dental practices, the study is designed to provide the practitioners with extensive support of the RC, the Study Manager, and the CC. Where possible, QA/QC will be assisted by or performed by the RC, the Study Manager, or the CC to allow the practitioner efforts to be focused on subject enrollment. Each practice will maintain an Eligible Patient Screening Log which captures whether a patient consented or not and will send a copy to the RC regularly, during Enrollment for Intensive Data Review. If a patient provides consent the date of consent will be recorded and if consent is not provided the reason for not consenting will be recorded.

3. Data Collection:

- a. The RAS will perform a QC review of the data collected on the first patient enrolled by each practitioner and provide feedback to the practitioner and practice. This early QC is a key component of assuring the quality of data collection at the practice, and data entry at the RAS.
- b. Further details regarding QA/QC of data collection are contained in the MOP..

4. Data Analysis and interpretation:

 All data analyses for presentations and publications will be verified by "secondary" programmer/statistician for 1) validity of statistical programming to correspondence with interpretation, and 2) appropriate analytic results (output) are correctly presented in presentation and/or publication.

5. Manuscript Writing, conference presentations:

a. The National Dental PBRN has a Publications and Presentations policy. The SPI will assure that this policy is followed for any manuscripts and conference presentations. This policy assures the quality of all National Dental PBRN manuscripts and presentations through the requirement of specific quality control steps prior to publication of any manuscript or other external publication/ presentation. Specifically the policy requires review and approval of manuscripts and presentations by the Publications & Presentations Committee.

Appendix C: Data Management Plan

The CC, for the study, Decision Aids for the Management of SOCL has Standard Operating Procedures (SOPs) which require the development of a Data Management Plan for each project for which the CC provides Data Management services. The CC SOPs require that the Data Management Plan be developed according to a standard template containing the following sections, where applicable:

Approval Signatures

Table of Contents

Abbreviations and Definitions

Dynamic References

1. Introduction

- 1.1 Protocol Summary
- 1.2 Data Management Services Plan

2. System and the Underlying Clinical Database

3. Network Directories

4. Data Validation Process

- 4.1 Univariate Alerts
- 4.2 Multivariate and Cross-Module Alerts
- 4.3 Edit Checks Development and Approval

5. Verification of System Setup and Implementation

- 5.1 System Specifications
- 5.2 User Acceptance Testing

6. Data Entry and Data Cleaning

- 6.1 Pre-Requisites for Site Data Entry
- 6.2 Granting Access to The Production Version of the System
- 6.3 Entering Data
- 6.4 Data Security
- 6.5 Quality Control Procedures
- 6.6 Query ("Discrepancy") Generation

7. Loading Electronic Files

8. Medical Coding

- 8.1 Adverse Event/Medical History Coding
- 8.2 Medication Coding

9. System Exported Database

- 10. Reports
- **11. SAE Reconciliation**

12. Changes to a Production System

13. System Closure

- 13.1 Closure Checks
- 13.2 Quality Assurance Audit and System Lock
- 13.3 System Unlock

14. Data Archiving and Provision of Final Materials to Sponsor

- 14.1 Database Archive
- 14.2 Study Materials and Data Transfer

15. DMP Associated Documents and SOP Reference Guide

Appendices

Appendix D: Study Timeline

Month 0 1 2 3 4 5 6 7 8 9 10 11 12 13 14 15 16 17 18 19 20 21 22 23 24

I-----I practitioner recruitment

I----I pre-intervention data collection (diagnostic vignettes)

I------I pre- intervention practitioner training (caries depth standardization, CRF completion)

I-----I pre-intervention data collection

I-----I practitioner randomization and device delivery, set up and training

I-----I post-randomization data collection (

I----- I study closeout-return devices

I-I post-clinical study data collection (diagnostic vignettes/ questionnaire)

Appendix E: Statistical Analysis

The primary analysis framework will be based on mixed-model logistic regression analysis, implemented with generalized estimating equations (GEE) to account for correlation among the clusters of observations made by the same practitioners and to provide valid comparisons among the study groups.

Initial exploratory analyses will be conducted for the entire study data set, in order to characterize the empirical distributions of each variable, to identify possible errors in the data, and to evaluate the proportion of missing values. Since the data for Specific Aims 1 through 3 are collected at a single time point, patient-level missing values are anticipated to be unlikely, compared to concerns that arise in studies that include follow-up. If a patient rescinds consent during the study procedures, the practitioner can recruit a replacement patient, as this will not affect the randomized intervention assignment.

The analyses will include all observations that have valid values for the variables in each of the respective analyses. No attempt to replace or impute values that are missing is planned, as this would require assumptions related to the associations that are to be investigated, and could allow pre-analysis expectations to influence the study findings. If a substantial number of missing values is observed, the distribution of these will be evaluated in order to determine whether the missingness can be reasonably assumed to be at random. If this situation holds, then missing values would reduce power, but would not bias the estimates. If missing values are found to occur non-randomly, then the mechanism leading to missing values must be taken into account in the analysis model, for instance, by including variables that are found to be related to missingness. The proposed sample size anticipates that some values may not be obtained, and provides for adequate power despite having up to approximately 20% of observations having missing values for some variables, depending on the differences and level of ICC that are actually observed in the study.

For evaluation of differences in proportions of lesions treated operatively among the intervention groups, the analysis data set will include all SOCLs that are enrolled by the study practitioners. The outcome variable for this analysis will be a dichotomous variable indicating whether the SOCL was treated operatively. Proportions of SOCL treated operatively will be calculated for each study arm. Confidence intervals, adjusted for correlation within clusters (practitioners), will be estimated from the GEE models. Statistical tests for differences in proportions among the three study arms will be based on Type III tests from the GEE analysis, controlling for the effect of clustering by practitioner. An indicator variable representing the study arm will be included as a fixed effect in this model, and a term representing the individual practitioners will be included as a random effect. The effect of regional site will be evaluated as a fixed effect, and will be included in the model if it explains a statistically significant portion of the observed variation in the outcome variable. The two pre-planned comparisons of the device versus no-device arms will be evaluated using contrasts, and will be tested using Chi-square tests of score statistics. Because these are pre-planned comparisons, each of these tests will be conducted at the 95% confidence level, using per-comparison error rates.

For the comparison of proportions of lesions treated operatively that have caries extending into dentin, the analysis data set will include all SOCLs that were treated operatively by the study practitioners. The outcome variable will be a dichotomous variable indicating whether the lesion extended into the dentin. The analysis will be identical to that utilized for Aim 1, except for the reduced analytic sample. GEE-based mixed-model logistic regression will be used to estimate confidence intervals for proportions of SOCLs extending into dentin, controlling for clustering by

practitioner and, if needed, for regional differences. Two pre-planned comparisons will be conducted using contrasts to compare each of the device study arms with the no-device arm.

The analysis data set for identification of clinical characteristics of SOCLs that predict caries extending into the dentin will include all SOCLs that were treated operatively by the study practitioners. The outcome variable will be a dichotomous variable indicating whether the lesion extended into the dentin. The primary statistical model will be mixed-model logistic regression, implemented with GEE in order to account for clustered observations. Clinical characteristics that will be evaluated as potential predictors of caries extending into dentin are luster, color, roughness on examination with explorer, tooth position (molar or premolar), and patient dental history variables. A term representing the individual practitioner will be included in the model as a random effect. Study arm, region and terms representing each of the clinical characteristics of the lesions will be included as fixed effects. Initial analyses will be conducted considering each of the clinical characteristic variables singly, along with region and the random effect term, to determine whether there is a significant "univariate" association between the potential predictor and the outcome. Following this series of analyses, a multi-variable approach will be used to evaluate the joint association between the clinical characteristics and the outcome. This analysis will include the practitioner term as a random effect, region, and all of the clinical characteristics that were associated with dentin involvement, at p < 0.10, in the "univariate" analyses. The liberal significance level, using p < 0.10, will be used in order to allow for the possibility that some variables may become more significant in the multivariable approach than in the "univariate" analyses. Further analysis may be conducted, in which non-significant predictors are removed from the multivariable model in order to obtain a more concise prediction model.

Additional descriptive analyses will be conducted to evaluate possible association of practitioner and patient characteristics with outcome measures or other study variables. Depending on the specific structures of these auxiliary analyses, appropriate analysis models may include hierarchical methods, or single-level approaches such as contingency table analysis using the Chi-square statistic or ordinary analysis of variance or logistic regression analyses.

For evaluation of differences in proportions of lesions treated operatively among the intervention groups, the analysis data set will include all SOCLs that are enrolled by the study practitioners. The outcome variable for this analysis will be a dichotomous variable indicating whether the SOCL was treated operatively.

For the comparison of proportions of lesions treated operatively that have caries extending into dentin, the analysis data set will include all SOCLs that were treated operatively by the study practitioners. The outcome variable will be a dichotomous variable indicating whether the lesion extended into the dentin.

Exploratory statistical analyses will be conducted to examine changes in practitioners' rates of operative treatment of lesions during the pre-randomization run-in period versus their rates during the post-randomization intervention period. Further analyses will be conducted to evaluate possible associations between pre- to post-randomization changes in practitioners' rates of operative treatment and variables representing practitioners' perception of changes in the decision-making process. This analysis will be conducted using the practitioner as the unit of analysis, and will utilize a mixed-model analysis of variance approach to evaluate changes in rates and to compare mean changes among the intervention groups, accounting for repeated observations for the practitioners.

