4 STUDY DESIGN

The study combines elements of a pre-and post-control group design and a randomized clinical trial. To achieve a sample of 1200 lesions for each of the three arms in the full study, we wish to enroll a total of 90 practitioners (total from all six regions) in the study, each of whom will enroll approximately 40 SOCLs (one lesion/patient), 20 enrolled/completed lesions during the pre-intervention phase, and 20 enrolled/completed lesions during the intervention phase. Thus, the patients enrolled will be representative of the patients with such lesions in the practitioners' offices.

Overview of Study Schedule

There will be a 4-8 month window for practitioner enrollment. When a practitioner has completed the study pre-enrollment requirements and the region has IRB approval s/he will be ready to begin the study. Following enrollment, as part of their study training, practitioners will be trained as follows:

- 1. Study Procedure Training: RCs will provide study procedure training, and practitioners will also receive a training manual which will serve as a reference and will highlight important information.
- 2. Standardization Training Pertaining to SOCLs: During the Study Procedure Training with the practitioner, the RC will provide photographs of teeth with SOCLs and review the clinical characteristics of SOCLs. The RC will answer any questions the practitioner might have about these characteristics. The photographs will be given to the practitioners to place in the operatory for review as needed.
- 3. Device Delivery and Set Up: Practitioners randomized to the device arm following the pre-intervention data collection phase will receive the devices from the RAS, and the RAS will assist with device set up.

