- 4. Device Familiarization: Practitioners randomized to the device arm will familiarize themselves on device use, thus simulating as closely as possible what occurs in practice if dentists purchase devices on their own. Practitioners will "self-train" according to manufacturer's instructions and manufacturer-provided materials (e.g. DVD, Webinar). Practitioners may seek further guidance on device use from their colleagues and may query a manufacturer representative. Device Familiarization will also involve practitioners familiarizing themselves with the devices through unsupervised clinical use with patients. This device familiarization period is anticipated to take approximately four weeks for all practitioners randomized into the device arms.

Before beginning the clinical portion of the study, practitioners will complete pre-study vignettes that require practitioners to make diagnostic decisions with scenarios and photos. They will be asked how likely they would be to choose a specific treatment procedure. This vignette will be completed online. Following the vignette, all practitioners will participate in an approximate 4 week long pre-intervention period without the assistance of a caries detecting device and will enroll patients with at least one lesion. Practitioners will record data for one lesion per patient, which will be determined randomly. If more than one lesion is found in one patient, practitioners will choose the tooth that is closest to the day of the month on the day they are observing the patient. They will choose the tooth in an ascending order. For example, if the day of the month is the fourth, the practitioner will choose the higher number tooth closest to the fourth. Data to be recorded include pre-treatment

findings, a treatment decision, and if necessary, post-treatment findings. If, during the first two weeks of the pre-intervention period, practitioners are unable to enroll five patients with a SOCL, or do not wish to further participate in the study, they may be withdrawn and new practitioner(s) will take their place prior to randomization. The goal for enrollment is approximately 20 enrolled/completed patients each with one SOCL.

Following the pre-intervention period, practitioners will be randomized into one of three arms (Spectra[®], DIAGNOdent[®], and no device). Practitioner randomization will occur after the pre-intervention period.

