Two outcomes are of interest: the proportion of all SOCL that are opened and the proportion of opened SOCL that are carious. Practitioners will each contribute 20 lesions to the study during the intervention period. The planned recruitment of 30 practitioners per group yields a total sample size of 600 lesions per group for the first outcome. The total sample size for the second outcome will be the number of lesions that are opened. Because the study design does not include follow-up of individual patients, patient-level dropout is not anticipated to be a major consideration. Drop-out of practitioners is possible, and could cause the loss of multiple observations, depending on the number of patients that are accrued prior to the practitioner drop-out, up to a maximum of 30. Part of the intent of the pre-intervention run-in period is to identify practitioners who are not likely to succeed in recruiting the required number of patients, and to provide an opportunity for practitioners to drop out prior to randomization, so that they can be replaced without interference to the randomization process. Still, it is possible that practitioners might drop out after randomization. Anticipating a severe situation in which 10% of the initial 30 practitioners in each group drop out prior to contributing any data, power and detectable difference calculations were repeated for 27 practitioners per group, and a total sample size of 540 lesions per group. While this is an extreme and unlikely occurrence, the additional tables provide an indication of the effect of a substantial loss of data.

The expected rates of lesion opening are 50% for no device and 30-35% for the device groups. Differences in rates of opening that would be detectable with 80% power are as follows:

Difference detectable with 80% power				ICC		
	0.00	0.01	0.02	0.03	0.04	0.05
Effective						
sample/group:	600	504	435	382	341	308
Detectable difference						
(%):	9.1	9.9	10.7	11.4	12.0	12.7
Rate in device group						
(%):	40.8	40.1	39.3	38.6	38.0	37.3

Assuming loss of 10% of practitioners per group, without contributing any data to the study:

Difference detectable with 80% power	ICC							
	0 0.01 0.02 0.03 0.04 0.0							
Effective comple/groups	E 40	454	204	244	207	077		
Effective sample/group:	540	454	391	344	307	211		
Detectable difference (%):	9.6	10.4	11.3	12.0	12.7	13.4		
Rate in device group (%):	40.4	39.6	38.7	38.0	37.3	36.6		

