11.3 Final Analysis Plan

This is the planned analysis based on the data we plan to collect. An appropriate statistical model must take into account both the level of measurement of the outcome variables and the study design. Both of the primary outcome variables, surgical treatment of the lesion and extension into dentin, may be appropriately represented as dichotomous variables. Each practitioner will be randomized to use a single device, or no device and no a priori study design levels defined within the level of practitioner. This approach yields a two-level hierarchical study design. A characteristic of this two-level model is the presence of correlation among the multiple observations obtained from each practitioner. The primary analysis framework will be based on mixed-model logistic regression analysis, implemented with generalized estimating equations (GEE), accounting for correlation among the clusters of observations made by the same practitioners. These models will include a term representing the individual practitioner as a random effect and study arm as a fixed effect. Additional control variables, including region, may be included if it is found that these are needed to account for possibly different distributions of practitioner or patient characteristics. Details of the analysis approach and related considerations are provided in Appendix E

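### The primary analysis sets are not limited to the intervention period, which contradicts the sample-size basis; run as written, both device contrasts would be diluted

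*Protocol*

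**What the plan says.** **Analysis sets.** For outcome 1 (operative treatment), Appendix E states that "the analysis data set will include all SOCLs that are enrolled by the study practitioners". The same definition stands in Section 11.3 and again near the end of Appendix E. For outcome 2 (extension into dentin), the same places take every lesion the study practitioners treated operatively. None of these definitions names a study period.

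**Which lesions count as enrolled.** Section 4 plans "20 enrolled/completed lesions during the pre-intervention phase, and 20 enrolled/completed lesions during the intervention phase" for each practitioner. The first 20 come from a "pre-intervention period without the assistance of a caries detecting device", and "Practitioner randomization will occur after the pre-intervention period".

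**Model.** Appendix E says: "An indicator variable representing the study arm will be included as a fixed effect in this model". Practitioner enters as a random effect, and region is added if significant. Section 11.3 allows further control variables to account for differing practitioner or patient characteristics, and describes a two-level design with "no a priori study design levels defined within the level of practitioner". No period term and no arm-by-period term is named. The comparison of rates before and after randomisation is exploratory (Section 11.3, Appendix E).

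**Sample size.** Section 11.2 counts 20 intervention-period lesions per practitioner. With 30 practitioners per group this "yields a total sample size of 600 lesions per group for the first outcome".

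**The concern.** The sets as worded and the set on which the trial was sized are different populations. Lesions assessed before randomisation had no device in any arm, so they carry no information on the device effect. If they are coded with the arm their practitioner later received, the arm contrast averages a null effect with the real one.

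The practitioner term does not prevent this. Arm is constant within practitioner, so both periods carry the same arm code, and only a period term with its interaction could separate them.

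Both primary estimates and the power claimed in Section 11.2 are at stake.

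**Working it through.** **Inputs.** All are from Section 11.2 unless noted:
- 30 practitioners per group
- 20 lesions each before and 20 after randomisation (Section 4)
- opening rates of 50% without a device and 30-35% with one
- ICC 0.00 to 0.05
- Bonferroni adjustment for two comparisons, so two-sided alpha 0.05/2 = 0.025
- per-comparison alpha of 0.05 in the analysis itself (Appendix E)

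**Step 1: reproduce the protocol's figures.** Effective n = 600/(1 + 19 × ICC) gives 600, 504, 435, 382, 341 and 308, exactly as tabulated. These values need 20 lesions per practitioner and 600 per group, that is, intervention-period lesions alone.

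Power = Φ[(|p1 − p2| − z × SE0)/SE1], where SE0 uses the pooled rate and SE1 the separate rates. For 50% vs 35% at n = 308 and alpha 0.025 (z = 2.241), SE0 = 0.0399 and SE1 = 0.0394. Power is Φ[(0.15 − 0.0893)/0.0394] = 93.8%, or 92.8% with a continuity correction. The protocol states about 92%.

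**Step 2: outcome 1 with the set as worded.** Assume equal phase sizes, a 50% rate in every arm before randomisation, and no change over time in the no-device arm.
- Device arm: (20 × 50% + 20 × 35%)/40 = 42.5%. The difference falls from 15 to 7.5 points.
- At the other end of the expected range, 30% becomes 40%, so 20 points fall to 10.
- On the log-odds scale, 0.49 and 0.48 of the effect remain.

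The lesion count rises to 1200 per arm with 40 per practitioner, so effective n = 1200/(1 + 39 × ICC). This takes one ICC across both periods. Power for 50% vs 35%, without continuity correction:

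| ICC | Intervention only, alpha 0.025 | Effective n, set as worded | Set as worded, alpha 0.025 | Set as worded, alpha 0.05 |
|---|---|---|---|---|
| 0.00 | 99.9% | 1200 | 92.6% | 95.8% |
| 0.01 | 99.5% | 863 | 81.2% | 87.9% |
| 0.02 | 98.8% | 674 | 69.9% | 78.9% |
| 0.03 | 97.6% | 553 | 60.3% | 70.6% |
| 0.04 | 95.9% | 469 | 52.5% | 63.5% |
| 0.05 | 93.8% | 407 | 46.2% | 57.4% |

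The extra lesions do not make up for the smaller difference at any ICC in the range.

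**Step 3: outcome 2 with the set as worded.** Section 11.2 expects 300 opened lesions in the no-device group and 210 in a device group, and takes 50% carious without a device. Assume that the pre-randomisation period adds 300 opened lesions per arm, 50% of them carious.
- Device arm, planned 65%: (300 × 50% + 210 × 65%)/510 = 286.5/510 = 56.2%. The difference falls from 15 to 6.2 points, so 0.41 of it remains.
- Power at ICC 0.00 and alpha 0.025 is 43%, against 87% in the protocol's table.

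**The case against.** The strongest reply is that an intervention-period analysis was plainly meant, and much of the text supports it:
- Section 11.2 sizes both outcomes on intervention-period lesions and calls the earlier phase a run-in.
- Appendix E speaks of differences among intervention groups, which exist only after randomisation.
- Appendix E describes the data for the first three aims as collected at one time point, and Section 11.3 describes a two-level design. Both fit a one-period data set.
- The comparison across periods is kept for a separate exploratory analysis.
- Back-up practitioners (Section 5.2) complete the pre-intervention phase and may never be randomised. Read literally, the set would contain lesions with no arm.

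This stands as evidence of intent, so the documents do not support reading the plan as a settled decision to pool. It also means that the missing period term is not a second defect, because a one-period analysis needs none. But none of these places limits the stated set, and the unrestricted wording occurs three times for outcome 1.

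A reader might also infer three stronger points that do not hold:
- **Sections 4 and 11.2 conflict over 1200 and 600.** They do not. "To achieve a sample of 1200 lesions for each of the three arms in the full study" covers both phases (30 × 40), and 600 covers the intervention period (30 × 20).
- **Adequate power is lost in every case.** At ICC 0.00 and 0.01 it stays above 80% even with the set as worded. The fall to 46% belongs to the top of the ICC range and to alpha 0.025. At the per-comparison 0.05 level it is 57%.
- **Both effects are exactly halved.** That is exact only for the outcome 1 risk difference under the assumptions in step 2. Outcome 2 is diluted more.

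**Conclusion.** The point holds as an internal contradiction: the stated primary analysis sets include pre-randomisation lesions assessed without a device, while the sample size rests on intervention-period lesions only. The harm is conditional on the text being followed literally. In that case the planned outcome 1 difference is 7.5 points instead of 15, and power at ICC 0.05 is about 46% (alpha 0.025) or 57% (alpha 0.05), against the stated 92% or so. The outcome 2 difference is about 6 points instead of 15. These figures rest on the protocol's planning rates, equal phase sizes and baseline rates, a common ICC across periods and, for outcome 2, the assumed yield of opened lesions before randomisation. Because both primary estimates depend on the definition, intent should not be left to inference.

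**What to change.** In Section 11.3, and at both places in Appendix E, define the two primary analysis sets as lesions enrolled in the post-randomisation intervention period (for outcome 2, those of them treated operatively). Use pre-intervention lesions only as baseline information, for example the practitioner's pre-intervention rate as a covariate. The alternative is to keep both periods, add period and arm-by-period terms, and name the arm-by-period contrast as the effect. Choose one of the two before the analysis.

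The 1200 in Section 4 needs no change. The cost is a few words in three places, with no new data and no change to the sample size. Consent dates are already logged (Appendix B), so each lesion can be placed before or after its practitioner's randomisation.
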